7 STUDY PROCEDURES

Refer also to Section 14: Schedule of Assessments

7.1 Day 1 (PRE-DOSE)

- Obtain informed consent.
- Verify eligibility per the inclusion and exclusion criteria. (See Sections 5.1 and 5.2)
 - Review and record medical history, including tobacco use, to ensure there are no exclusionary illnesses.
 - Review and record concomitant medications for possible prohibited medications. (See Section 6.7)
- If subject is female of child-bearing potential and meets inclusion criteria 11.c, obtain urine pregnancy test and proceed if result is negative.
- Measure and record vital signs (BP, HR, Temp, Resp).
- Collect and record SPO2 by Finger Sensor
- Perform Physical exam (may be done by the Principal Investigator or their designee)
- Complete baseline symptom survey to establish severity of symptoms (if present)
- Collect oropharyngeal swab for virologic testing (RT-PCR) and resistance analysis.
- Collect two nasal swabs for antigen testing and molecular viability testing.
- Collect blood samples for
 - Uric acid
 - CRP
 - Hematology and clinical chemistry laboratory analyses (samples collected within 48 hours of enrollment are acceptable):
 - Resistance analysis
 - Optional: Antibodies to SARS-CoV-2.
 - Optional: Biobanking
 - Optional: Pre-dose PK

- Perform subject randomization (via EDC) to establish treatment arm (favipiravir + SOC or placebo + SOC).
- Explain in home procedures for the study (self-sampling of nasal swabs, temperature, SPO2, completing the daily questionnaire and the optional collection of stool sample).
- Provide supplies to research subject and review the calendar of return visits.
- Optional: Explain that stool sample from first bowel movement after enrollment should be collected in Zymo fecal tube and brought back to Day 5 follow-up visit. If the first bowel movement sample cannot be collected, it is permitted to collect a subsequent bowel movement sample.

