5 SUBJECT POPULATION

5.1 Inclusion Criteria

The following criteria must be confirmed as “YES” except optional PK, antibody, and stool sample collection:

1. Adults (18 to 80 years old inclusive)
2. Diagnosis of COVID-19 disease:
 - a. If symptomatic without signs of respiratory distress (as defined by SpO₂ \geq 94% on room air, RR \leq 20, HR \leq 100), with FDA-cleared molecular diagnostic assay positive for SARS-CoV-2 within 72 hours from swab to the time of commencing informed consent. Mild disease is defined as having at least 1 of the following:
 - i. Fever ($>98.7^{\circ}\text{F}$)
 - b. Cough/Shortness of breath/dyspnea
 - c. Fatigue
 - d. Headache/Body aches
 - e. Joint pain
 - f. Chest pressure
 - g. GI symptoms including nausea, vomiting, and/or diarrhea
 - h. Abdominal pain
 - i. Sore throat
 - j. Nasal congestion
 - k. Chills
 - l. Runny nose
 - m. New loss of taste or smell
 - n. Abdominal pain
 - o. Rash
 - p. If asymptomatic, initial diagnosis obtained no more than 72 hours from initial swab to the time of commencing informed consent
3. Subject or their legal representative understands the requirements of the study and provides written informed consent prior to undergoing any treatment-related procedures.
4. Subject agrees to take daily nasal swabs (anterior nares) for Day 1 to Day 10 and Day 14, 21, and 28 using the study provided materials, and mail via FEDEX each sample on the day collected.
5. Subject agrees to record daily symptoms, temperature, oxygen saturation, and pulse using the study provided materials.
6. Subject agrees to obtain stool samples after the Day 1 visit, and 1-3 days before the Day 14 and Day 28 timepoints and agrees to bring the sample back in the provided stool collection kit to their subsequent appointment and to optionally mail in 4-month sample. Collection of stool is optional for sites.
7. Subject agrees to return to the study site for follow-up visits on Day 5, 10, and 28. The study site will be staffed by trained healthcare providers wearing full personal protective equipment and study site equipment will be disinfected between patients according to the same protocols

as a clinical setting. Subjects will be wearing masks, will be appropriately spaced, and the number of subjects assessed at each time will be limited.

8. Subject agrees to maintain home or other quarantine as recommended by the study physician, except to visit the study site as required by the protocol.

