9. Members of the same household may participate in the study as long as the inclusion and exclusion criteria are met.
10. If male, subject must:
 - a. Be sterile (e.g., have had a vasectomy at least 6 months prior to Day 1 dosing), OR,
 - b. Agree not to donate sperm during the study and for seven days following the last dose of study medication, AND,
 - c. Agree to strictly adhere to the following contraceptive measures during the study and for seven days following the last dose of study medication:
 - i. Abstain from sexual intercourse.
 - ii. Use a condom during sexual intercourse with a female of child-bearing potential. In addition, the female partner must use another form of contraception (e.g. intrauterine device [IUD], diaphragm with spermicide, oral contraceptives, injectable progesterone, or subdermal implants).
11. If female, subject must:
 - a. Be unable to bear children (have not had a period for ≥ 12 consecutive months, have had her uterus or ovaries removed, or have had a tubal ligation), OR,
 - b. Must ensure that their male partner is incapable of fathering a child (e.g., has had a vasectomy at least 6 months prior to study entry), OR,
 - c. If she is of childbearing potential will strictly adhere to the following contraceptive measures during the study and for seven days following the last dose of study medication:
 - i. Abstain from sexual intercourse, OR,
 - ii. Must ensure that her male partner agrees to use a condom during sexual intercourse and agree to use an approved method of contraception (e.g., IUD, diaphragm with spermicide, oral contraceptives, injectable progesterone, or subdermal implants).
 - d. Agrees to stop breast-feeding prior to first dose of study drug and through seven days after completing therapy.
 - e. Has a negative urine pregnancy test at screening.
 - f. Has not had unprotected sexual intercourse within the past month.

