5.2 Exclusion Criteria

All criteria must be confirmed as “NO”:

1. Subject has a concomitant bacterial respiratory infection, as defined by positive respiratory culture
2. Subject has a history of abnormalities of uric acid metabolism unless cleared
3. Subject has a history of hypersensitivity to an anti-viral nucleoside-analog drug targeting a viral RNA polymerase
4. Subject has any of the following abnormal laboratory test results at screening:
 - a. Platelet count $<100,000$ cells/mm³
 - b. Absolute lymphocyte count <500 cells/mm³

- c. Hemoglobin <11 g/dL for women and <12 g/dL for men
 - d. Serum creatinine concentration $\geq 1.5 \times$ ULN
 - e. Confirmed creatinine clearance (CrCl) < 50 mL/min by Cockcroft-Gault
 - f. Serum uric acid >20mg/dL
5. Subject is using adrenocorticosteroids (except topical or inhaled preparations or oral preparations equivalent to or less than 10 mg of oral prednisone) or immunosuppressive or immunomodulatory drugs (e.g., immunosuppressants, anticancer drugs, interleukins, interleukin antagonists or interleukin receptor blockers).

NOTE: Treatment of study participants following institutional COVID-19 treatment policies or guidelines, including the use of immunomodulatory medications, is permitted. This excludes treatment with agents that have the potential for direct antiviral activity, including convalescent plasma and NO, and co-enrolment into other clinical studies that evaluate investigational agents for COVID-19.

6. Subject has a serious chronic disease (e.g., human immunodeficiency virus [HIV], cancer requiring chemotherapy within the preceding 6 months, moderate or severe hepatic insufficiency and/or unstable renal, cardiac, pulmonary, neurologic, vascular, or endocrinologic disease states per investigator judgement).
7. Has previously received favipiravir within the past 30 days.
8. Has renal insufficiency requiring hemodialysis or continuous ambulatory peritoneal dialysis (CAPD).
9. Has liver impairment greater than Child-Pugh A. (NOTE: Child-Pugh A subjects will have the maintenance dose decreased to 800 mg BIID).
10. Has a history of alcohol or drug abuse in the previous 6 months.
11. Has a psychiatric disease that is not well controlled where controlled is defined as: stable on a regimen for more than one year.
12. Has taken another investigational drug within the past 30 days.
13. Is deemed by the Investigator to be ineligible for any reason.

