6 STUDY TREATMENT - FAVIPIRAVIR

6.1 Study Drug

Favipiravir will be provided in 200 mg tablet form to be stored at controlled room temperature (15°C to 30°C [59°F to 86°F]) and shielded from light. Matching placebo will be provided in tablet form to be stored at controlled room temperature (15°C to 30°C [59°F to 86°F]) and shielded from light.

Standard Dose

Subjects randomized to the favipiravir + SOC arm will be administered loading doses of 1800 mg BID (ideally 12 hours apart but 10-16 hours is allowed) on Day 1, and then maintenance dosing of 800 mg twice daily BID (Ideally 12 hours apart but 10- 16 hours is allowed) on Days 2-10 beginning 24 hours after the first dose. Day 1 is deemed to be the first 24 hours after enrollment into the study, with time 0 (time of first dose) occurring as soon as possible after the subject's eligibility has been confirmed.

An exception to the above maintenance dose will be made for those subjects entering the study with a Child-Pugh liver impairment of grade A who will receive favipiravir 600 mg BID on Days 2 through 10.

Subjects randomized to the placebo + SOC arm will be administered placebo BID (ideally 12 hours apart but 10-16 hours is allowed) on Day 1, and then maintenance dosing twice daily BID (Ideally 12 hours apart but 10- 16 hours is allowed) on Days 2-10 beginning 24 hours after the first dose. Day 1 is deemed to be the first 24 hours after enrollment into the study, with time 0 (time of first dose) occurring as soon as possible after the subject's eligibility has been confirmed.

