7.2 Day 1 (FIRST DOSE AND POST-DOSE)

NOTE: Day 1 is deemed to be the first 24 hours after enrollment into the study, with time 0 (time of first dose) occurring as quickly as possible after the subject's eligibility has been confirmed.

- Administer first dose (1800 mg favipiravir or placebo) at time 0.

Following First Dose:

- Monitor patient for 30 minutes after their first dose.
- Optional: Take a blood sample 45 to 75 minutes following the first dose for post-dose PK analysis

7.3 Days 5, 10, 28 (Follow-up) or Early Termination (Window of +1 or -1 day allowed on Days 5 and 28. Window of -1 allowed for Day 10.)

- Conduct and record the results of a Physical Exam (Day 5, 10, 28).
- Review and record concomitant medications (Note: if there have been changes in concomitant medications during the study, determine whether the change is due to an AE).
- Measure and record vital signs (BP, HR, Temp, Resp).
- Collect and record SPO2 by Finger Sensor
- Collect oropharyngeal swab for virologic testing (RT-PCR) and resistance analysis.
- Collect and record adverse events (see Section 8.4 for detailed instructions).
- Collect nasal swab for antigen testing and molecular viability testing (day 1, 5, 10)
- Collect blood samples for:
 - Hematology and clinical chemistry laboratory analyses (Day 5, 10, 28)
 - Urine for repeat pregnancy test (Day 5)
 - Optional: Antibodies to SARS-CoV-2. (28)
 - Optional: Biobanking (28)
 - Optional: Blood for PK and resistance analysis obtained pre-dose (within 30 minutes prior to dosing) and post-dose (45 to 75 minutes following dosing) (Days 5 and 10).
- Optional: Provide Zymo fecal stool collection kit: one on Day 1, two on Day 10, and 28.

- Optional: Collect stool samples on Day 5, 14, 28, and patient sends in sample at 4 months post enrollment date.

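### The Section 7.1 Day 1 instruction ties the pre-dose pregnancy test to inclusion 11.c, so it is narrower than 11.e and the Schedule and misses a possibly fertile woman entering under 11.b

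*Combined protocol and SAP*

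**What the plan says.** The Day 1 pre-dose list in Section 7.1 contains this instruction: "If subject is female of child-bearing potential and meets inclusion criteria 11.c, obtain urine pregnancy test and proceed if result is negative". It sets two joint conditions, child-bearing potential and meeting 11.c.

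Section 5.1, item 11, gives three routes of entry for women, joined by OR:
- 11.a: she cannot bear children.
- 11.b: "Must ensure that their male partner is incapable of fathering a child", for example because of a vasectomy at least 6 months before entry.
- 11.c: she is of child-bearing potential and follows the listed contraceptive measures.

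Items d, e and f follow with no connecting word. Item e reads "Has a negative urine pregnancy test at screening" and does not mention 11.c.

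The 5.1 list opens with "The following criteria must be confirmed as" YES, apart from optional sampling. Section 7.1 also says "Verify eligibility per the inclusion and exclusion criteria". Section 6.1 has "time 0 (time of first dose) occurring as soon as possible after the subject's eligibility has been confirmed", and Section 7.2 says much the same: "occurring as quickly as possible after the subject's eligibility has been confirmed".

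The Schedule of Assessments (Section 14) marks a urine pregnancy test on Days 1 and 5 and names no population. Section 7.3 lists a repeat test at Day 5, also without restriction. Synopsis inclusion 5 asks a woman to fulfil one item of a list running from a to e, in which e is the negative pregnancy test.

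**The concern.** The 7.1 instruction carries out an eligibility criterion but covers fewer women than the criterion appears to. The group left out is women who qualify through their partner's infertility and do not also meet 11.c. Such a woman may be fertile. Her partner's status bears on conception during the study, but it does not show that she is not already pregnant on Day 1.

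This matters because Section 2.2 refers to embryo-fetal toxicity studies and says that favipiravir is not recommended in pregnancy. Staff working down the Day 1 list would find the test tied to 11.c, with the instruction to go on only after a negative result attached to that same line. If a site followed the line literally and missed 11.e, a woman entering under 11.b could receive her first dose without a test.

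**Working it through.** No arithmetic applies and the plan states no figure to reproduce. The check is to compare, for each route of entry, what each text requires on Day 1.

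| Route of entry | 7.1 instruction | 11.e as a separate criterion | 11.e as part of 11.c only | Synopsis 5, read literally | Schedule, Day 1 |
|---|---|---|---|---|---|
| 11.a only | not ordered | required | not required | not required | marked, population not named |
| 11.b only | not ordered | required | not required | not required | marked, population not named |
| 11.c | ordered | required | required | not required | marked, population not named |

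1. **The 7.1 instruction.** Both of its conditions must hold. A woman entering under 11.b only fails the second, even if she is fertile.

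2. **How 11.e attaches.** Item e is lettered at the same level as a, b and c, while the sub-items of c are numbered i and ii. No connector joins c to d. The natural reading is therefore that e stands alone and applies to a woman entering under 11.b. On that reading 7.1 is narrower than 5.1, and the two conflict. The other reading, in which d to f belong to c, fits the wording of 7.1 but has to ignore the lettering. On that reading 7.1 and 5.1 agree, and neither asks for her test.

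3. **The eligibility check.** On the natural reading, all 5.1 criteria must be confirmed, 7.1 says to verify them, and the first dose follows confirmed eligibility (6.1, 7.2). Skipping the test would be an eligibility deviation.

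4. **The Schedule.** Section 7 opens by referring the reader to Section 14. The first-dose and post-dose list in 7.2 contains no pregnancy test, so the Day 1 mark fits the pre-dose list. It has no 11.c limit and so favours testing. It cannot apply to every subject, because men are enrolled, so staff must look elsewhere for who is tested.

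5. **The synopsis.** Read literally, meeting b alone satisfies inclusion 5. The same reading would admit a woman who met only d (stopping breast-feeding), which cannot be intended. The wording is defective, but it leaves the reach of the test unclear.

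**The case against.** The strongest reply is that the protocol already deals with this elsewhere. Item 11.e has no 11.c condition, every 5.1 criterion must be confirmed before dosing, the Schedule marks a Day 1 test without restriction, and a repeat test at Day 5 presupposes an earlier one. A missed test would then be a site error. Most of this stands, and it limits the point to a conflict between texts.

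It does not remove the conflict. The 7.1 line is the procedural text that says who is tested on Day 1 and makes going on depend on the result, and it says so too narrowly. The synopsis leaves the question open as well.

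A reader might infer three stronger things, and the documents support none of them:
- *That women entering under 11.b may be dosed untested.* Item 11.e and the eligibility check point the other way. Only the weaker reading of item 11, or a literal reading of the synopsis, leaves room for it.
- *That pregnancy is no bar to entry.* None of the 13 exclusions in Section 5.2 names it, the last being the general "Is deemed by the Investigator to be ineligible for any reason", and Section 5.3 lists it as a reason for stopping. But a mandatory negative test among the inclusion criteria does the work of an exclusion.
- *That 11.e and the 7.1 line are the sole pre-dose checks.* The Day 1 mark in the Schedule is another.

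**Conclusion.** The point holds as a minor internal conflict in a safety check. The 7.1 instruction is narrower than 11.e and the Day 1 Schedule mark, and it leaves out a possibly fertile woman who enters under 11.b without meeting 11.c. The wording of 7.1 is certain. The practical consequence is less so, because it rests on how items d to f of 5.1 attach to a, b and c. On the more natural reading, the eligibility check should still produce the test.

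The documents do not say how many women would enter under 11.b, so no frequency is estimated. Harm would need a woman entering by that route who is pregnant at entry, a test missed despite 11.e and the Schedule, and allocation to favipiravir. Alpha, power and the primary analysis are unaffected.

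**What to change.** **Section 7.1.** Delete the condition that ties the test to 11.c, so that every woman of child-bearing potential (any woman not meeting 11.a) is tested. Cite 11.e, and require a negative result before randomisation.

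**Section 5.1 item 11 and synopsis inclusion 5.** State that the negative test (e) is required in addition to a, b or c for every woman of child-bearing potential. All three places then cover the same women.

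**What to leave alone.** Do not turn d to f into a blanket requirement for all women. Item 11.f bars recent unprotected intercourse. Applied to women who qualify under 11.a or 11.b, it could exclude those who used no contraception because they or their partner are infertile, which would undercut those two routes.

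**One point for the sponsor to confirm.** If 11.e is now meant for all women, the new wording drops the test for those who meet 11.a. Section 7.1 does not order a test for them today either. If the sponsor wants them tested, 7.1 must say so too; otherwise the mismatch only moves to another group.

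**Cost.** Wording in three places, and at most one urine test per woman entering under 11.b.

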7.2 Day 1 (FIRST DOSE AND POST-DOSE)

NOTE: Day 1 is deemed to be the first 24 hours after enrollment into the study, with time 0 (time of first dose) occurring as quickly as possible after the subject's eligibility has been confirmed.

- Administer first dose (1800 mg favipiravir or placebo) at time 0.

Following First Dose:

- Monitor patient for 30 minutes after their first dose.
- Optional: Take a blood sample 45 to 75 minutes following the first dose for post-dose PK analysis

7.3 Days 5, 10, 28 (Follow-up) or Early Termination (Window of +1 or -1 day allowed on Days 5 and 28. Window of -1 allowed for Day 10.)

- Conduct and record the results of a Physical Exam (Day 5, 10, 28).
- Review and record concomitant medications (Note: if there have been changes in concomitant medications during the study, determine whether the change is due to an AE).
- Measure and record vital signs (BP, HR, Temp, Resp).
- Collect and record SPO2 by Finger Sensor
- Collect oropharyngeal swab for virologic testing (RT-PCR) and resistance analysis.
- Collect and record adverse events (see Section 8.4 for detailed instructions).
- Collect nasal swab for antigen testing and molecular viability testing (day 1, 5, 10)
- Collect blood samples for:
 - Hematology and clinical chemistry laboratory analyses (Day 5, 10, 28)
 - Urine for repeat pregnancy test (Day 5)
 - Optional: Antibodies to SARS-CoV-2. (28)
 - Optional: Biobanking (28)
 - Optional: Blood for PK and resistance analysis obtained pre-dose (within 30 minutes prior to dosing) and post-dose (45 to 75 minutes following dosing) (Days 5 and 10).
- Optional: Provide Zymo fecal stool collection kit: one on Day 1, two on Day 10, and 28.

- Optional: Collect stool samples on Day 5, 14, 28, and patient sends in sample at 4 months post enrollment date.

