2.2 Preclinical and In Vitro Experiences

Preclinical and animal studies indicate that favipiravir is effective against RNA viruses causing a variety of disorders.

Preclinical and animal studies show no direct suppression of white blood cell types or immunosuppression by favipiravir. This contrasts with strong immunosuppressive effects of ribavirin and other antiviral agents.

Genotoxicity studies indicate that favipiravir does not pose a clinical genotoxic risk, however, based on the results of embryo-fetal toxicity studies, favipiravir is not recommended for use in pregnant females, those who may become pregnant, or those who are nursing. A human testicular toxicity study was run to determine if there are effects on human spermatogenesis. No abnormality in testicular function tests was observed; however, this study was performed at doses less than those to be used in this study. Due to the effect on embryo-fetal development seen in animals, and the presence of favipiravir in semen for several days after the end of therapy, the recommendation is

for male and female contraception for seven days following the end of treatment, in the dose regimen for influenza. Details of the reproductive toxicity studies may be found in the Investigator’s Brochure.

Favipiravir is both metabolized by, and inhibits, aldehyde oxidase (AO). A potential interaction exists between favipiravir and drugs oxidatively metabolized by the AO pathway, where blood concentration of these drugs or favipiravir may be increased. Similarly, a potential interaction exists between favipiravir and drugs inhibiting AO activity, where blood concentration of favipiravir may be increased. Similarly, a potential interaction exists between favipiravir and drugs inhibiting AO activity, where blood concentration of favipiravir may be increased. Favipiravir should not be used with pyrazinamide.

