5.3 Removal of Subjects from Treatment

The participation of a subject in the study or the administration of treatment may be terminated at any time for one of the following reasons:

- The subject desires to discontinue study treatment.
- The subject withdraws consent to participate in the study.
- The subject is unwilling or unable to comply with the safety procedures.
- The subject is discovered to be pregnant.
- The subject experiences a medical emergency that necessitates withdrawal.
- The subject is withdrawn at the discretion of the Investigator for medical reasons or non-compliance.
 - AST or ALT > 8 x ULN
 - ALT or AST > 3 x ULN AND total bilirubin > 2X ULN
 - AST or ALT > 3 x ULN AND patient has right upper quadrant pain or eosinophilia

- Uric acid >20mg/dL CrCl < 30

A subject whose treatment is terminated should remain in the study for appropriate follow up assessments whenever possible.

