6.3 Outpatient Favipiravir Dosing

Subjects in the favipiravir + SOC arm, will be dispensed sufficient favipiravir to ensure continued dosing until their next study visit. Subjects in the placebo+ SOC arm, will be dispensed sufficient placebo to ensure continued dosing until their next study visit. Subjects in both arms will also be given a Diary Card to record the date and time they take their dose.

Subjects will also be instructed that if they miss a dose, they should follow the guidelines:

- 1) If more than 1/2 the time until their next dose has elapsed, they SHOULD NOT take the dose. They should just take the next dose at the normal scheduled time.
- 2) If less than 1/2 the time until their next dose has elapsed, they should take the missed dose immediately.
- 3) In both cases, they should then return to their regular dosing schedule.
- 4) The intention is to complete a 10-day course of medication. If, because of missed doses, there are leftover doses after completing their PM dose on Day 10, bring all additional doses to their next study visit.

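### Pregnancy tests stop at Day 5, so if a test takes 6 or more days from conception to turn positive (assumed), none can detect a conception during dosing or the 7-day washout (minor)

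*Combined protocol and SAP*

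**What the plan says.** **Hazard.** Section 2.2 advises against use in pregnancy because of embryo-fetal toxicity studies. Its contraception advice rests on embryo-fetal effects in animals and on "the presence of favipiravir in semen for several days after the end of therapy".

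**Exposure period.** Section 6.3 has participants finish treatment by "completing their PM dose on Day 10". Criterion 11.c in Section 5.1 requires women of child-bearing potential to follow "contraceptive measures during the study and for seven days following the last dose of study medication". Criterion 10 sets the same period for men who are not sterile.

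**Tests.** Section 7.1 has a Day 1 pre-dose step for a woman of child-bearing potential who "meets inclusion criteria 11.c, obtain urine pregnancy test and proceed if result is negative". Section 7.3 lists "Urine for repeat pregnancy test (Day 5", and the Day 5 visit may fall on Days 4 to 6. The pregnancy-test column in Section 14 is marked in the Day 1 and Day 5 rows only.

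**Action on a positive test.** Section 5.3 lists "The subject is discovered to be pregnant" among the reasons for ending treatment or participation.

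**Later contact.** Clinic visits also take place on Days 10 and 28, with blood drawn at each: "Hematology and clinical chemistry laboratory analyses (Day 5, 10, 28". No clinic visit is scheduled after Day 28.

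**The concern.** The plan names a reproductive hazard and sets a contraception period to match it, but its testing ends about halfway through dosing. A woman who conceives during dosing or washout could leave the study at Day 28 without knowing she is pregnant after exposure to a drug the plan advises against in pregnancy. A male participant's partner could be in the same position.

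What is at stake is telling the participant and recording the exposed pregnancy. Exposure itself is not at stake, because any test late enough to find these conceptions comes after the last dose. The primary endpoint, the power and the planned safety comparisons are unaffected.

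**Working it through.** The plan gives no figure to reproduce, so this is day arithmetic.

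**Inputs from the protocol.** Last dose Day 10 (6.3); washout 7 days (11.c); repeat test on Days 4 to 6 and last visit on Days 27 to 29 (7.3); planned enrolment 180, randomised 1:1 (9.2).

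**Inputs assumed.** The lag from conception to a positive test, the share of women, the share who can conceive, the share of men with a partner who can conceive, and the conception risk. The documents give none of these.

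**Window.** 10 + 7 = Day 17, so 17 days: 10 of dosing and 7 of washout.

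**Coverage.** Latest detectable conception day = test day − lag. Days are counted straight through, so Day 0 is the day before Day 1.

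| Lag (days) | Test on Day 4 | Day 5 | Day 6 | Window days covered, of 17 |
|---|---|---|---|---|
| 3 | 1 | 2 | 3 | 1–3 |
| 4 | 0 | 1 | 2 | 0–2 |
| 5 | −1 | 0 | 1 | 0–1 |
| 6 | −2 | −1 | 0 | 0 |
| above 6 | earlier | earlier | earlier | 0 |

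Six days is the break point. Even at 3 days, no washout day is covered. The Day 1 test reaches only 1 − 6 = Day −5 at a 6-day lag.

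**Same formula for a test at the Day 28 visit.**

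| Lag (days) | Test on Day 27 | Day 28 | Day 29 | Window days covered, of 17 |
|---|---|---|---|---|
| 8 | 19 | 20 | 21 | 17 |
| 10 | 17 | 18 | 19 | 17 |
| 12 | 15 | 16 | 17 | 15–17 |
| 14 | 13 | 14 | 15 | 13–15 |

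All 10 dosing days stay covered up to a 17-day lag (27 − 17 = 10). A Day 10 test would do much less: it reaches 10 − 6 = Day 4 at a 6-day lag and no dosing day at a lag of 10 or more.

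**Expected number of exposed conceptions (all rates assumed).**
- Women: half of 180 is 90. Entry is open to "Adults (18 to 80 years old inclusive", so not all can conceive. Taking 30–60% as meeting 11.c gives 27–54, of whom half, 13.5–27, are on favipiravir. At 0.1–1% conception risk: 0.0135–0.27.
- Partners: 45 men on favipiravir × 30–60% = 13.5–27. At the same risk: 0.0135–0.27.
- Total: 0.027–0.54.

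**The case against.** The strongest reply is that nothing in the protocol says testing must span the contraception period. Contraception is the preventive measure. The Day 1 test excludes an existing pregnancy, and the Day 5 test catches one that Day 1 missed while treatment can still be stopped. That is correct. A reader might infer that the plan contradicts itself or that the Day 5 test is useless; the documents support neither.

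The second reply is that safeguards exist. Criterion 11.c requires abstinence, or a condom together with an approved method. Criterion 11.f requires no unprotected intercourse in the preceding month. Section 8.4.5 makes a congenital anomaly in the offspring of a treated subject an SAE, which on its wording can include a male participant's child. Section 8.4.4 requires SAEs to be reported to 46 days post-dose (10 + 46 = Day 56, counted from the last dose), and possibly drug-related ones after that with no end date. A reader might therefore infer too much from the gap, namely that birth defects would go unreported. The text does not support that. What remains is narrower: 11.f concerns conceptions before dosing, contraception does not detect its own failure, and SAE reporting depends on someone coming forward. Adverse events are queried up to Day 28 (8.4.1), but the visible text does not list pregnancy itself as reportable.

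Third, the consent pages were removed from this copy, and the Investigator's Brochure and the manual of procedures (MOP) are not available here. Any of them may ask participants to report a pregnancy. That limits what can be said about reporting, but it does not add a test to the schedule in Sections 7.3 and 14.

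Fourth, the expected yield is below one event and every rate behind it is assumed. This stands, and it is why the point is minor.

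**Conclusion.** The point holds as a minor, inexpensive safety improvement. For any lag of 6 days or more, scheduled tests cover 0 of the 17 days from first dose to the end of washout. With a shorter lag of 3 to 5 days they reach at most Day 3 and never the washout. The lag is the one assumption this conclusion needs.

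The practical size is small: 0.03 to 0.54 expected exposed conceptions, counting participants and partners, so the true number is most likely zero. A reader might infer that a later test would protect a fetus from exposure or alter the trial's findings. It would do neither: Days 27 to 29 fall 17 to 19 days after the last dose, and no efficacy result or planned safety comparison depends on it. The gain is that an exposed pregnancy would be found, the participant told and the sponsor informed.

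Criterion 11.c also says that contraception applies during the study, which could mean to Day 28. On that reading, a Day 28 test at lags of 8 to 14 days reaches Day 13 to Day 21 of 28. Days 1 to 17 remain the part relevant to drug exposure.

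**What to change.** In Section 7.3 and the Section 14 schedule, add a urine pregnancy test at the existing Day 28 visit, in both arms, for women meeting 11.c. At the same visit, ask each participant one question: is there any known pregnancy in the participant or, for men, in a partner? Tell the participant of a positive result and notify the sponsor; the contact route in Section 8.4.6 would serve. Contact after Day 28 about the outcome of a pregnancy is optional and not part of this recommendation.

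**Cost.** One urine test for about 27 to 54 women (assumed) and one question per participant, with no new visit, blood draw or analysis.

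**Limits.** At a 14-day lag, conceptions after Days 13 to 15 are still missed, and a partner's late conception may not be known by Day 28.
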